##### **6.4.3.2 AEs and SAEs**

AEs will be summarized using MedDRA System Organ Class and preferred terms. Tables will show by treatment group the number and percentage of participants experiencing an AE within a System Organ Class or within preferred term category by severity or by relationship to study product. For the calculations in these tables, a participant with multiple AEs within a category will be counted once under the maximum severity or the strongest recorded causal relationship to study product. Formal statistical testing comparing groups is not planned since interpretation of differences must rely heavily upon clinical judgment.

A listing of SAEs reported to the DAIDS Regulatory Support Center (RSC) Safety Office will provide details of the events including severity, relationship to study product, time between onset and last vaccination, and number of vaccinations received.

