**Table 3-1 Schema**

| Study arm | n   | MVA/HIV62B dose                    | AIDSVAX B/E dose (B/E/Alum) | Prior HVTN 205 regimen | Boost (deltoid) M0 (Day 0)              | Boost (deltoid) M4 (Day 112)            |
|-----------|-----|------------------------------------|-----------------------------|------------------------|---|---|
| Group 1   | 20  | $1 \times 10^8$ TCID 50 | 0                           | MMM*                   | MVA/HIV62B (left) + Control (right)     | MVA/HIV62B (left) + Control (right)     |
| Group 2   | 20  | $1 \times 10^8$ TCID 50 | 300/300/600 mcg             | MMM                    | MVA/HIV62B (left) + AIDSVAX B/E (right) | MVA/HIV62B (left) + AIDSVAX B/E (right) |
| Group 3   | 20  | $1 \times 10^8$ TCID 50 | 0                           | DDMM**                 | MVA/HIV62B (left) + Control (right)     | MVA/HIV62B (left) + Control (right)     |
| Group 4   | 20  | $1 \times 10^8$ TCID 50 | 300/300/600 mcg             | DDMM                   | MVA/HIV62B (left) + AIDSVAX B/E (right) | MVA/HIV62B (left) + AIDSVAX B/E (right) |
| Group 5   | 20  | 0                                  | 300/300/600 mcg             | DDMM                   | Control (left) + AIDSVAX B/E (right)    | Control (left) + AIDSVAX B/E (right)    |
| Total     | 100 |                                    |                             |                        |   |   |

\* Denotes a prime-boost vaccine regimen comprising 3 sequential administrations of MVA/HIV62B.

\*\* Denotes a vaccine regimen comprising 2 sequential priming administrations of JS7 DNA plasmid followed by 2 sequential boost administrations of MVA/HIV62B.

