## Duration per participant

10 months of scheduled clinic visits (main study) followed by a participant health contact at 2 years following the initial study injection

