## 5 Objectives and endpoints

### 5.1 Primary objectives and endpoints

*Primary objective 1:*

To evaluate the safety and tolerability of MVA/HIV62B and AIDSVAX B/E given separately or together as boost injections after prolonged immunologic rest, to participants who received MVA/HIV62B vaccinations in DDMM and MMM regimens in HVTN 205

*Primary endpoint 1:*

Frequency and severity of local and systemic injection site reactogenicity signs and symptoms, for each boost regimen

Laboratory measures of safety: white blood cells (WBC), neutrophils, lymphocytes, hemoglobin, platelets, ALT, AST, alkaline phosphatase, and creatinine

Frequency of AEs categorized by MedDRA System Organ Class, and MedDRA Preferred Term, severity and assessed relationship to study products; detailed description of all AE meeting DAIDS criteria for expedited reporting

Number of participants with early discontinuation of vaccinations and reason for discontinuation

*Primary objective 2:*

To compare HIV-specific antibody responses elicited by MVA/HIV62B and AIDSVAX B/E given separately or together as boost injections after prolonged immunologic rest

*Primary endpoint 2:*

Frequency, magnitudes and isotypes of Env-specific Ab responses for gp120, gp41, V1/V2, and the IDR of gp41 at 2 weeks after each boost

Neutralizing Ab titers and breadth against the Env vaccine strain (ADA) and heterologous tier 1 and tier 2 strains at 2 weeks after each boost

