#### **9.4 Follow-up visits**

The following procedures are performed at all scheduled follow-up visits:

- Risk reduction counseling (as described in Section 9.7);
- Pregnancy prevention assessment (as described in Section 9.2 and 9.8); and
- Assessment of new or unresolved social impacts (site staff will ask participant about the status of any unresolved social impacts and if s/he has experienced any new social impacts as a result of the trial participation);
- Assessment of new or continuing concomitant medications (as described in Section 9.2);
- Cardiac symptom assessment; and
- Assessment of new or unresolved AEs/intercurrent illnesses.

Additional procedures will be performed at scheduled follow-up visits as specified in Appendix G:

- Administration of the social impact assessment questionnaire (types of impacts assessed involve personal relationships, health insurance, life insurance, educational or employment opportunities, housing, immigration, or travel);
- Administration of a questionnaire that asks the participant about any HIV testing he or she may have received outside of the study;
- HIV infection assessment including pre-test counseling. A subsequent follow-up contact is conducted to provide post-test counseling and to report results to participant;
- Confirm that participants received HIV test results from previous visit. If not, provide test results and post-test counseling as appropriate;

- Abbreviated physical examination including weight, vital signs, and a symptom-directed evaluation by history and/or appropriate physical exam based on participant self-reported symptoms or complaints;
- Complete physical examination, including weight, vital signs, and clinical assessments of head, ears, eyes, nose, and throat; neck; lymph nodes; heart; chest; abdomen; extremities; neurological function; and skin;
- Urine or serum pregnancy test (for participants who were born female). Persons who are NOT of reproductive potential due to having undergone total hysterectomy or bilateral oophorectomy (verified by medical records), are not required to undergo pregnancy testing;
- Optional mucosal specimen collection
- Clinical laboratory tests including:
  - CBC with differential and platelet count,
  - Chemistry panel (Section 9.2),
  - ECG and Cardiac troponin (if clinically indicated). and
  - Urine dipstick (urinalysis if appropriate; see Section 9.9);

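### Non-serious unsolicited clinical AEs are tabulated with no onset window after either boost, so a short-lived post-boost excess would be diluted in the Section 6.4.3.2 tables

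*Combined protocol and SAP*

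**What the plan says.** AE frequency belongs to primary endpoint 1 in Section 5.1: "Frequency of AEs categorized by MedDRA System Organ Class", with further breakdown by preferred term, severity and relationship.

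Section 6.4.3.2 gives the summary: "Tables will show by treatment group the number and percentage of participants experiencing an AE within a System Organ Class" or preferred term, by severity or relationship. The counting rule is that "a participant with multiple AEs within a category will be counted once under the maximum severity" or the strongest recorded relationship. On inference, "Formal statistical testing comparing groups is not planned". The section gives no onset window, no split by boost and no person-time denominator. Timing appears there only in the SAE listing, which includes "time between onset and last vaccination".

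Section 3 gives follow-up as "10 months of scheduled clinic visits (main study"), and Appendix G puts the last visit at Day 303. Section 9.4 requires at every scheduled follow-up visit: "Assessment of new or unresolved AEs/intercurrent illnesses". Boosts fall on Day 0 and Day 112 (Table 3-1, column "Boost (deltoid) M4 (Day 112")). All five groups receive MVA/HIV62B, AIDSVAX B/E or both.

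Other safety data keep their timing:
- Solicited reactions are collected on the vaccination day and for 3 full days after each boost (Section 9.10). The summary in 6.4.3.1 then takes the maximum over both injection visits.
- Laboratory abnormalities are tabulated at each postvaccination timepoint (Section 6.4.3.3).
- Events not on the reactogenicity form, or starting after day 3, go to the adverse experience log (Section 9.10) and so into the undivided AE table.

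**The concern.** Any reaction to a boost is most likely in the weeks after injection. A table that counts a participant once per category, whenever the event began, mixes that period with a much longer one in which most events are background. A real but short-lived excess then appears as a small difference in a large percentage, and the table cannot show whether events cluster after injection.

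This matters more here than in a placebo-controlled trial. No arm is unboosted, so an effect common to both products cancels in every between-group comparison. Relationship coding helps only in part, because it is a case-by-case judgement by blinded site staff. AE frequency is a primary endpoint, and Sections 4.8 and 4.8.4 say that the combination of the two products has not been given to humans. Since no test is planned and differences are left to clinical judgement, the layout of the table is the analysis.

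**Working it through.** **1. The plan's own safety figures.** Section 6.1.1 gives the true rate for a 90% chance of at least one event. With p = 1 − 0.1^(1/n), n = 20 gives 10.87% (stated 10.9%) and n = 40 gives 5.59% (stated 5.6%). Both reproduce. They concern the probability per participant of an event and fix no period.

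**2. Inputs from the documents.** Boosts on Days 0 and 112; last visit on Day 303; 20 participants per group, and 40 in combined Groups 1+3 and 2+4.

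**3. Assumptions, not in the documents.** A 28-day window after each boost; a 5% background probability per 28 days for an AE category; that probability doubled to 10% in each window. The windows cover 56 of 303 days (56/303 = 18%), leaving 247 days (82%).

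**4. Dilution.** The follow-up holds 303/28 = 10.82 periods of 28 days.

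| | No boost effect | With boost effect | Ratio | Difference |
|---|---|---|---|---|
| Whole study | 1 − 0.95^10.82 = 42.6% | 1 − 0.95^8.82 × 0.90² = 48.5% | 1.14 | 5.9 points |
| Windows only | 1 − 0.95² = 9.8% | 1 − 0.90² = 19.0% | 1.95 | 9.2 points |

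With a background of 3% to 8% per 28 days, the whole-study ratio is 1.16 down to 1.11 and the windowed ratio 1.97 down to 1.92.

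**5. Different assumptions.** Take a constant hazard with 10% to 60% of participants having an event over 303 days, a threefold rate in the window, and windows of 14 or 28 days. The whole-period ratio is then 1.10 to 1.34 and the windowed ratio 2.6 to 3.0. At 40% background with 28-day windows, the whole period moves from 40.0% to 50.3% and the windows from 9.0% to 24.7%.

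**6. Detection artefact in an in-window versus out-of-window ratio.** Appendix G schedules post-boost CBC and chemistry on Days 14, 126 and 196. Days 14 and 126 are each 14 days after a boost, so two draws fall in the 56 window days and one in the other 247. With equal risk per draw and no vaccine effect, the rate ratio is (2/56)/(1/247) = 8.8. Post-boost dipsticks are on Days 14 and 126 only, both inside the windows, so the denominator rate is zero. Section 6.4.3.3 sends reportable laboratory abnormalities without a clinical diagnosis into the AE tables, so this would affect them.

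**7. Precision of a within-participant ratio, clinical AEs only.** Under the assumptions in step 3:
- Group 5 expects 20 × 2 × 0.10 = 4 events inside the windows and 20 × 0.05 × 247/28 = 8.8 outside. At 4 and 9 events, the ratio is 2.0 with exact 95% CI 0.4 to 7.0.
- Groups 1+3 expect 8 and 17.6. At 8 and 18 events, the ratio is 2.0 with exact 95% CI 0.7 to 4.7.

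**The case against.** A reader might infer that all post-boost harm loses its timing. The documents do not support that: solicited reactions, laboratory values and SAEs are captured or reported close to injection, and cardiac symptoms are asked about at every visit after screening. The gap is confined to non-serious unsolicited clinical AEs.

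A reader might also infer that the trial has no reference rate. That goes too far. Group 4 can be compared with Groups 3 and 5 among prior DDMM recipients, and Group 2 with Group 1 among prior MMM recipients. Randomisation balances background in each comparison, and each isolates what one product adds. Section 6.1.1 quotes a placebo SAE rate of about 4%, though for SAEs only and without an observation time. What remains is that an effect shared by both products has no unboosted reference for non-serious AEs.

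The whole-study period is an inference, since 6.4.3.2 names none. A separate SAP could specify a window, and no such text is among the documents. However, the only safety rule that Section 6.4 leaves to the SAP concerns participants given the wrong treatment.

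The strongest remaining argument is that this is a descriptive phase 1 table, supported by weekly safety-team review and unblinded board review about every 4 months, and that onset can be tabulated later. The gain is also modest in absolute terms: 9 points against 6. Even windowed, Fisher's exact test of 9.8% against 19.0% would have power of only 0.14 (40 v 40) or 0.10 (40 v 20). This limits the point to presentation and interpretation. It does not justify leaving the timing of a primary endpoint to a decision made after unblinding.

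**Conclusion.** The point stands for non-serious unsolicited clinical AEs, mainly those starting after day 3 or not on the reactogenicity form. On the plan's natural reading, a doubling confined to 28 days after each boost would show as a ratio of 1.14 instead of 1.95. Across the assumptions tried, the whole-period ratio lies between 1.10 and 1.34. The background rates, the size of the effect and the window length are all assumed, so these figures show the direction and rough scale of the dilution and do not forecast it.

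A pooled within-participant rate ratio over all AEs would look like an obvious remedy, but it is not sound here. The sampling schedule alone would give about 8.8 for blood abnormalities with no vaccine effect. Restricted to clinical AEs it is usable only as a description. Its interval is wide, four of the seven post-enrolment visits (Days 7, 14, 119 and 126) fall within 14 days after a boost, and the comparison time is not true unboosted background, because all of it follows the first boost.

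**What to change.** Keep the whole-study table and state its period. Add to Section 6.4.3.2 a descriptive table of unsolicited clinical AEs with these features:

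- **Onset category:** within a pre-specified window after boost 1, within the same window after boost 2, and all other main-study time. The sponsor sets and justifies the window; 28 days is only illustrative.
- **Layout:** each of the five groups and each boost regimen (1+3, 2+4, 5), with person-time denominators.
- **Exclusion:** leave AEs found only by scheduled laboratory or urine tests out of the in-window versus out-of-window comparison. They remain in the whole-study table and the Section 6.4.3.3 summaries.
- **Interpretation:** rest it on between-group comparisons within the window. Any within-participant rate ratio should cover clinical AEs only, be labelled descriptive, and carry its 95% CI and the caveat that visits are denser after each boost.

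The cost is SAP wording and one more table, built from AE onset dates, which the plan already needs for the SAE listing and for separating reactogenicity from later events. It needs no new visit, sample or participant.

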#### 6.1.1 Sample size calculations for safety

The goal of the safety evaluation for this study is to identify safety concerns associated with product administration. The ability of the study to detect SAEs (Section 9) can be expressed by the true event rate above which at least 1 SAE would likely be observed and the true event rate below which no events would likely be observed. Specifically, for each vaccine group of the study ( $n = 20$ ), there is a 90% chance of observing at least 1 event if the true rate of such an event is 10.9% or more; and there is a 90% chance of observing no events if the true rate is 0.5% or less. For vaccine groups 1 and 3 combined and groups 2 and 4 combined ( $n = 40$ ), there is a 90% chance of observing at least 1 event if the true rate of such an event is 5.6% or more; and there is a 90% chance of observing no events if the true rate is 0.2% or less. As a reference, in HVTN vaccine trials from December 2000 through April 2014, about 4% of participants who received placebos experienced an SAE.

Probabilities of observing 0, 1 or more, and 2 or more events among groups of size 20 and 40 are presented in Table 6-1 for a range of possible true AE rates. These calculations provide a more complete picture of the sensitivity of this study design to identify potential safety problems with the vaccine.

**Table 6-1 Probability of observing 0 events, 1 or more events, and 2 or more events, among groups of size 20 and 40, for different true event rates**

| True event rate (%) | Pr(0/20) | Pr(1+/20) | Pr(2+/20) | Pr(0/40) | Pr(1+/40) | Pr(2+/40) |
|---------------------|----------|-----------|-----------|----------|-----------|-----------|
| 1                   | 81.8     | 18.2      | 1.7       | 66.9     | 33.1      | 6.1       |
| 3                   | 54.4     | 45.6      | 12        | 29.6     | 70.4      | 33.8      |
| 5                   | 35.8     | 64.2      | 26.4      | 12.9     | 87.1      | 60.1      |
| 7                   | 23.4     | 76.6      | 41.3      | 5.5      | 94.5      | 78        |
| 9                   | 15.2     | 84.8      | 54.8      | 2.3      | 97.7      | 88.6      |
| 10                  | 12.2     | 87.8      | 60.8      | 1.5      | 98.5      | 92        |
| 20                  | 1.2      | 98.8      | 93.1      | < 0.1    | > 99.9    | 99.9      |
| 30                  | 0.1      | 99.9      | 99.2      | < 0.1    | > 99.9    | > 99.9    |

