| 40                  | < 0.1    | > 99.9    | 99.9      | < 0.1    | > 99.9    | > 99.9    |

An alternative way of describing the statistical properties of the study design is in terms of the 95% confidence interval (CI) for the true rate of an AE based on the observed data. Table 6-2 shows the 2-sided 95% confidence intervals for the probability of an event based on a particular observed rate. Calculations are done using the score test method [31]. If none of the 40 participants receiving a MVA/HIV62B only boost (groups 1 and 3 combined) or MVA/HIV62B + AIDSVAX B/E boost (groups 2 and 4 combined) experience a safety event, the 95% 2-sided upper confidence bound for the true rate of such events is 8.8%. For each individual vaccine group (n = 20), the 2-sided upper confidence bound for this rate is 16.1%.

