### 11.2.3 Expedited reporting of adverse events to DAIDS

Requirements, definitions and methods for expedited reporting of AEs are outlined in Version 2.0 (January 2010) of the *Manual for Expedited Reporting of Adverse Events to DAIDS* (DAIDS EAE Manual), which is available on the RSC website at <http://rsc.tech-res.com/safetyandpharmacovigilance/>. The SAE Reporting Category will be used for this study.

The internet-based DAIDS Adverse Experience Reporting System (DAERS) must be used for expedited AE reporting to DAIDS. In the event of system outages or technical difficulties, expedited AE reports may be submitted via the DAIDS EAE Form. For questions about DAERS, please contact [[contact]](mailto:[contact]) or from within the DAERS application itself.

Sites where DAERS has not been implemented will submit expedited AE reports by documenting the information on the current DAIDS EAE Form. This form is available on the RSC website: <http://rsc.tech-res.com/safetyandpharmacovigilance/>. For questions about expedited AE reporting, please contact the RSC ([[contact]](mailto:[contact])).

The study products for which expedited reporting are required are:

- MVA/HIV62B and control for MVA/HIV62B
- AIDSVAX B/E and control for AIDSVAX B/E

In addition to the expedited Reporting Category identified above, other AEs that must be reported in an expedited manner are: all myopericarditis events.

While the participant is in the main study reporting period (Section 3), the SAE Reporting Category will be used.

If the participant has completed the main study and is in the “annual health contact reporting period” (Section 3) the SUSAR Reporting Category will be used. In addition, per Section 9.5, all adverse events that are serious are collected on the LTFU Event Log and reported to the SDMC.

After the participant has completed the annual health contact period and is off study, sites must report SUSARS if the study site staff becomes aware of the events on a passive basis (eg, from publicly available information).

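### After the main study, the SAE listing in 6.4.3.2 takes in only SUSARs and myopericarditis, so no planned output identifies the other late serious events as serious

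*Combined protocol and SAP*

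**What the plan says.** Section 6.4.3.2 describes two kinds of AE output. The first is a set of tables by treatment group, by MedDRA class or preferred term, split by severity or by relationship to product. Each participant counts once per category. The second is the SAE listing: "A listing of SAEs reported to the DAIDS Regulatory Support Center (RSC) Safety Office will provide details of the events". Its fields include severity, relationship, time from last vaccination to onset, and number of vaccinations received.

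What reaches the RSC is set in 11.2.3. For the first period: "While the participant is in the main study reporting period (Section 3), the SAE Reporting Category will be used". For the annual health contact period, "the SUSAR Reporting Category will be used". All myopericarditis is expedited in addition. The same section has every serious adverse event in the later period entered on the LTFU Event Log and sent to the SDMC.

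Section 3 sets the two periods: "10 months of scheduled clinic visits (main study) followed by a participant health contact at 2 years following the initial study injection". Section 9.6 lists the events asked about at that contact, including hospitalizations, and has adverse events assessed for relationship.

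Primary endpoint 1 in 5.1 asks for a "detailed description of all AE meeting DAIDS criteria for expedited reporting". Section 6.1.1 frames safety sensitivity in terms of SAEs without reference to cause: "The ability of the study to detect SAEs (Section 9) can be expressed by the true event rate above which at least 1 SAE" can be expected. It adds, for reference, that "about 4% of participants who received placebos experienced an SAE".

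**The concern.** The listing is defined by a reporting route, and the route narrows partway through follow-up. Before the change, a serious event is listed whatever its cause. After it, apart from myopericarditis, an event is listed only if it was judged both related and unexpected. A reader of the final report could take the listing to be complete through Month 24 when it is complete only through the main study.

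What is at stake is the completeness of the final safety account by group. Section 4.8 says the MVA/HIV62B plus AIDSVAX B/E combination has not been tested in humans, and Groups 2 and 4 receive it. A listing that does not depend on attribution lets a reader look across groups for a pattern that judging events one at a time could miss. Section 6.1.1 also discusses SAEs of any cause, which the listing no longer shows once the main study ends.

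**Working it through.** This is a question of scope, and the plan states no figure to reproduce. The check follows the text and then the calendar.

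**1. Which events are in the listing**

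| Period | Goes to the RSC (11.2.3) | Goes to the SDMC | In the 6.4.3.2 listing |
|---|---|---|---|
| Main study, to about Day 303 | All SAEs | All AEs (11.2.2) | All SAEs |
| Annual health contact period, to Day 728 | SUSARs and all myopericarditis | All serious AEs, on the LTFU Event Log | SUSARs and myopericarditis only |

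The documents do not spell out SUSAR. I use the usual meaning, a suspected (related) and unexpected serious reaction. This agrees with 11.2.3, which describes the FDA reports as covering unexpected SAEs related to product. Section 11.2.3 cites 9.5 for the late collection, but the health contact is in 9.6.

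**2. Whether another output in 6.4.3 identifies the remaining late events as serious**

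Reactogenicity covers the day of vaccination and three full days after it (9.10). The laboratory outputs and the discontinuation table do not classify events by seriousness. That leaves the AE tables, and several passages suggest the late events would enter them:
- Section 6.4 describes the final analysis and covers all data from enrolled participants.
- The AE definition in 11.2.2 carries no time limit.
- Section 11.2.2 sends all AEs to the SDMC.
- Section 9.6 supplies the relationship assessment that the tables use.

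However, the tables are split by grade or relationship only. A Grade 4 or 5 event would stand out by grade. A lower-grade hospitalization would look like any other event of that grade. Because each participant counts once at maximum severity, a late event could also be hidden by an earlier one of equal or higher grade in the same category.

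**3. The window affected** (visit days from Appendices F and H)

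- Length: 728 − 303 = 425 days, and 425/728 = 58% of the time from first injection to the Month 24 contact.
- Nominal gap from the second boost to the start of the window: 303 − 112 = 191 days.

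**4. The number of events**

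The documents give no SAE rate for this window. As an assumption only, if 1% to 4% of 100 participants had a serious event in it, 100 × 0.01 = 1 to 100 × 0.04 = 4 participants would be affected, before removing those whose events were SUSARs or myopericarditis. The upper end borrows the placebo figure in 6.1.1, whose observation period is not stated. The range shows scale and is not a forecast.

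**The case against.** The strongest reply is that the listing does what the protocol asks. Primary endpoint 1 calls for detail on events meeting the expedited criteria, and the listing gives those SAEs. This stands. A reader might infer that 6.4.3.2 contradicts the endpoint, and it does not.

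The second reply is that the late events are not missing from the analysis, because the natural reading of 6.4, 6.4.3.2, 9.6 and 11.2.2 puts them in the by-group AE tables. This largely stands. What it leaves is the absence of any marker of seriousness.

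The third concerns size. A reader might infer that one unlisted event changes a group's reported SAE rate and its interval, because 6.1.1 says of the case with no events: "For each individual vaccine group (n = 20), the 2-sided upper confidence bound for this rate is 16.1" percent. The documents do not support this. Section 6.4.3 plans no SAE rate and no SAE confidence interval by group, and Table 6-2 is a design-stage illustration. The 4% placebo figure is no firm yardstick either, since nothing shows that it includes events recalled at a two-year contact.

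The fourth is that participants remain protected. The events start about 191 days or more after the second boost, SUSARs and all myopericarditis stay in the listing, quarterly review continues under 11.4.3, and unrelated Grade 5 SAEs go immediately to the PSRT under Table 11-1. This also stands. A reader might infer that data are lost or that monitoring stops, but the text shows neither. Monitoring still differs from a final account by group: the scheduled unblinded SMB reports in 6.4.5.1 belong to the main study, and 11.4.3 describes no review by arm.

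**Conclusion.** The point holds as a minor gap in scope. Followed as written, 6.4.3.2 lists all SAEs through the main study but only SUSARs and myopericarditis from about Day 303 to Day 728. Other serious events in that window are held by the SDMC, and no planned output identifies them as serious. No primary comparison, planned estimate, pause rule or participant protection changes.

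The number of affected events is unknown and probably small. The conclusion rests on the usual meaning of SUSAR, since the DAIDS reporting manual is not among the documents, and on reading the listing sentence literally. The 191-day and 425-day figures are nominal, because visit windows are set in the Study Specific Procedures. The change is worth making because it is cheap and the events are already collected.

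**What to change.** Replace the listing sentence in 6.4.3.2 with wording to this effect:

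*All SAEs in the SDMC database, from main-study CRFs and from the LTFU Event Log through the Month 24 contact, will be listed by treatment group whatever their DAIDS reporting category. Events reported to the RSC will be flagged. Events after the main study will be shown separately, with the number of participants reached at Month 24.*

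Keep the existing detail fields. The flag preserves the expedited-reporting part of primary endpoint 1.

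The cost is a few sentences and one extra data source in the listing, with no new visits, data collection or sample size. The downside is data quality. Late events rest largely on recall at a single contact, which is why they belong in a separate section. Section 9.6 names neither grade nor onset date, and the LTFU Event Log form is not in the documents, so severity and time from last vaccination may be blank for some of them.
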